2.1.3 Safety Objectives

To compare the following between intervention and control arms:

- (a) Summarise incidence of injurious falls as indicated by peripheral fractures, summarised by home
- (b) Compare mortality rates in intervention and control homes.

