3 STUDY METHODS

3.1 Overall study design and plan

Target for randomisation: 77 RNHs (78 actual)
Date of first randomisation: 19th February 2009
Date of last randomisation: 30th April 2010

Trial design: cluster randomised, parallel group

Blinding: Clinical researchers were blinded to allocation to interpret records on

deaths.

Randomised Interventions: exercise programme + depression awareness programme vs. control

intervention (Depression awareness programme)

Planned allocation ratio: 2 intervention homes: 3 control homes

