5 GENERAL ISSUES FOR STATISTICAL ANALYSIS

All analyses will be conducted two-sided and significance interpreted at the 5% level.

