5.8 Method for handling clustering effects

We will use mixed effects models with a random effect for RNH.

It is possible that there may be additional clustering effects in intervention homes only, because the exercise classes are group activities and there may be therapist effects. However, exactly who delivered each class in not recorded, though each home's activities are overseen by a primary therapist who has the most influence on how the classes are run. It is not possible to disentangle these effects, if they exist, as physiotherapists on annual or sick leave were replaced temporarily by other physiotherapists.

Therefore, we will simply quantify and describe the clustering for each outcome overall by study arm and present 95% confidence intervals for these to check if there is substantially greater clustering in the intervention arm than in the control arm.

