9.3 Secondary analysis

The analysis strategy is the same as for the co-primary outcomes.

- Remission of depression: reduction in proportion of participants depressed in the intervention arm. A mixed effects logistic model will be defined. This will be fitted using the xtmelogit command.
- Cognitive function Mini Mental State: We will compare the rate of change in MMSE cluster mean at baseline and at end of intervention in exercise and control homes.
 We could construct linear mixed effects models with MMSE at 0, 6, and 12 months, with random effects for RNH. This will be fitted using the xtmixed command.
- EQ-5D: we will use linear mixed models, with RNH as a random effect. This will be fitted using the xtmixed command.
- Mobility: (SPPB) we will use linear mixed models, with RNH as a random effect.
 This will be fitted using the xtmixed command.
- Falls

Binary fear of falling: reduction in proportion of participants declaring fear of falling in the intervention arm. A mixed effects logistic model will be defined. This will be fitted using the *xtmelogit* command.

- Pain: 5-point scale. Ordinal mixed effects logistic regression (either in Stata using the gllamm command or in MLWiN.)
- The Social Engagement Scale uses six items from the Minimum Data Set residential assessment instrument (MDS-RAI). Ordinal mixed effects logistic regression (either in Stata using the *gllamm* command or in MLWiN.)

The following outcomes will not be modelled. However, medication use and hospital admissions are important for the health economic analysis (see separate analysis plan).

- Medication use (descriptive statistics only)
- · Hospital admissions (descriptive statistics only)
- All-cause mortality.

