10.5 Serious adverse events

According to the 'adverse event reporting protocol', an SAE is any untoward or medical occurrence that: results in death or is life threatening or requires hospitalisation or results in persistent disability of incapacity or requires medical intervention to prevent one of these (or is otherwise considered medically significant by the investigator).

SAEs can be classified as directly attributable (i.e. occur during a study assessment or getting to or from or occur during a group-activity session), or indirectly attributable (i.e. at any other time between randomisation and end of follow-up).

Table 6 Classification of anonymised fracture-related deaths, and fractures data.

Deaths* and Fractures (indivdiual level data)	Attribution of SAE			
	direct	indirect		
study participant (intervention)	A, E	otherwise		
non study participant (partaking in exercise)	E	otherwise		
study particpant (control)	Α	otherwise		

A = during study assessment

E = during exercise

otherwise = not (A or E)

Difference in rates of peripheral fractures between intervention and control homes (mixed effects Poisson model with resident-time in study as the exposure variable). This will be fitted using the *xtmepoisson* command.

Reporting of cause of death data

All deaths in residents will be reported and documented. We will have data on deaths amongst all residents from all homes. This will not provide accurate dates of death and characteristics of residents. We will conduct a simple comparison of total death rate in the two trial arms. For those who have consented/assented to have their data used, we will have exact date of death from death certification data, plus age and gender and all the other baseline variables. For this group we will construct Kaplan-Meier plots and carry out log-rank tests to see if there is any difference in all cause mortality over time. We will also consider using Cox's proportional hazards models (streg command) or logistic regression to allow for covariates depending on the number of deaths.

All cause of death data will be based on ICD10 coding provided by MRIS. These deaths data are provided as the underlying cause of death and also as the factors contributing to death.

^{*} fracture-related deaths (ICD10 chapter S)

This is a safety analysis that will be presented for all subjects contributing data to the study.

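### The log-rank test planned for all-cause mortality makes no allowance for clustering by home, so its p-value is too small if deaths cluster

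*SAP*

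**What the plan says.** SAP 2.1.3 sets a safety objective: "Compare mortality rates in intervention and control homes". Section 10.5 gives the methods.

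- **All residents**, for whom accurate dates of death are not available: "We will conduct a simple comparison of total death rate in the two trial arms". No method is named.
- **Consented or assented residents**, with exact dates of death: the team will "construct Kaplan-Meier plots and carry out log-rank tests to see if there is any difference in all cause mortality over time". Cox or logistic models are only to be considered, to allow for covariates and depending on the number of deaths. The Cox model is tied to the `streg` command.
- **Fracture-related deaths**: a 95% confidence interval for the difference in rates, with no method named.
- **Peripheral fractures**, in the same section: a mixed-effects Poisson model with resident-time as exposure.

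The general rule in 5.8 is "We will use mixed effects models with a random effect for RNH". Table 5 gives the fracture outcome a random effect for home but has no row for mortality. Section 9.3 puts all-cause mortality in the list headed "The following outcomes will not be modelled". Section 5.2.4 sets person-time in the home as the denominator for deaths, so that residents who were not present throughout can be included. Section 5 adds: "All analyses will be conducted two-sided and significance interpreted at the 5% level".

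**The concern.** The home is the unit of randomisation, and the SAP inflates every sample size for clustering. Homes differ in type, from local authority to private nursing, so differing death rates between homes are plausible. A log-rank test takes its variance from individual residents. If deaths cluster, that variance is too small and a chance difference between arms is declared significant too often.

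The SAP cites mortality of up to 34% a year in this population, so there will be enough deaths for the test to be read seriously. What is at stake is a false signal of harm or benefit on one of the two stated safety comparisons. The co-primary analyses are not touched, and no stopping rule depends on mortality.

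**Working it through.** **1. The SAP's own clustering arithmetic.** Design effect DE = 1 + (m − 1) × ICC, where m is the mean cluster size.

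- Table 3, ICC 0.05: m = 15.0, 5.4 and 4.5 give 1.70, 1.22 and 1.175. These equal the printed factors.
- Table 4, ICC 0.053: m = 9.6, 7.5 and 3.9 give 1.456, 1.345 and 1.154, against 1.46, 1.34 and 1.16 printed.

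The formula is therefore the one the SAP uses.

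**2. Cluster size for the consented group.** Table 4 gives 9.6 per home after 10% loss and 7.5 after 30% loss. 9.6/0.9 = 10.7 and 7.5/0.7 = 10.7, so m = 10.7 before loss. Later joiners would raise this, so m = 15 (Table 3) is shown as well.

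**3. Mortality ICC.** The SAP gives none. The 0.05 was set for the sample-size outcomes and the 0.053 comes from baseline GDS-15. A range of 0.01 to 0.05 is assumed.

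**4. True two-sided error of an unadjusted test at nominal 5%:** 2 × [1 − Φ(1.96/√DE)].

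| m | ICC (assumed) | DE | √DE | True error |
|---|---|---|---|---|
| 10.7 | 0.01 | 1.097 | 1.047 | 6.1% |
| 10.7 | 0.02 | 1.194 | 1.093 | 7.3% |
| 10.7 | 0.05 | 1.485 | 1.219 | 10.8% |
| 15 | 0.01 | 1.140 | 1.068 | 6.6% |
| 15 | 0.02 | 1.280 | 1.131 | 8.3% |
| 15 | 0.05 | 1.700 | 1.304 | 13.3% |

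**5. Check on the log-rank test itself.** The formula is an approximation for survival data, so the test was simulated with no treatment effect. Each setting had 4,000 runs, with 31 v 47 homes (78 split 2:3), about 10.7 residents per home, an assumed one joiner per home at each of 3, 6 and 9 months, 34% annual mortality and log-normal home frailty. Late joiners entered the risk set on joining.

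Frailty SD can be put roughly on the ICC scale. With hazard h = −ln(0.66) = 0.4155, ICC ≈ (h × 0.66)² × SD² / (0.34 × 0.66) = 0.0752 × SD² / 0.2244.

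| Frailty SD | Approximate ICC | Rejection rate |
|---|---|---|
| 0 | 0 | 4.8% |
| 0.2 | 0.013 | 6.2% |
| 0.3 | 0.030 | 9.2% |
| 0.45 | 0.068 | 14.4% |
| 0.6 | 0.121 | 20.0% |

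The test holds its level without clustering and loses it as clustering grows, in line with step 4.

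**6. Late entry, with no home clustering.**

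- Equal joining in both arms: rejection was 4.8% with delayed entry, 5.0% with each resident's own entry as origin, and 4.6% when joiners were counted from home randomisation.
- Unequal joining (assumed 0.5 v 1.5 per home per visit): 4.9%, 4.5% and 18.0% respectively.

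Harm needs both unequal joining and counting joiners from home randomisation.

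**The case against.** The strongest reply is that 5.8 states a general rule, and that naming no method is different from planning one without clustering. This stands in part for the total death rates and the fracture-related interval, which could be analysed with a home effect. It does not rescue the log-rank test, which cannot hold a random effect. Section 9.3 also tells the analyst that mortality is not modelled, which discourages reading 5.8 into the rate comparison.

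A second reply is that the size is assumed. This stands: at the low end the error is 6.1% against 5%, and without clustering there is no fault.

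A reader might infer more than the document supports:

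- **That late entry is mishandled.** Section 5.2.4 already gives deaths a person-time denominator. For the log-rank test the SAP is silent on time origin and entry. That is a gap, not a stated error, and step 6 shows harm only under two conditions that the SAP does not state.
- **That all-cause mortality intervals are too narrow.** None is planned. The only interval for a death outcome concerns fracture-related deaths.
- **That error exceeds 20% for all residents.** At 32 per home and ICC 0.05 the formula gives 22%. But 32 beds is a size cut-point, not a mean occupancy, and the method for that comparison is not stated.
- **That 9.3 contradicts 2.1.3.** Rates can be compared without a model. The loose end is between 9.3 and the optional models in 10.5.
- **That `streg` spoils the result.** It is Stata's parametric survival command, so it is the wrong name for a Cox model, but the slip sits in an optional analysis.

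**Conclusion.** The point holds for the log-rank test. It is the only named test of all-cause mortality, it ignores the unit of randomisation, and it departs from the SAP's own rule and from its treatment of fractures in the same section. For the consented group at 10.7 residents per home, the true two-sided error is about 6% to 11% instead of 5%. This rests on an assumed mortality ICC of 0.01 to 0.05 and on a cluster size derived from Table 4. The direction is certain if deaths cluster by home; the amount is not known. The total death-rate comparison and the fracture-related interval are under-specified and would have the same fault if computed crudely. The missing time origin, the mismatch between 9.3 and 10.5, and the command name are smaller matters to settle in the same edit.

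**What to change.** In 10.5:

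- Base the mortality test for consented or assented residents on a Cox model (`stcox`) with home-clustered robust variance or shared frailty by home. Keep the Kaplan-Meier plots as description.
- Compare total and fracture-related death rates with the home random-effect Poisson model already planned for fractures, using the person-time exposure of 5.2.4.
- State the time origin, and let residents who join after randomisation enter the risk set only when they come under observation, consistent with 5.2.4.
- Replace `streg` by `stcox` where the Cox model is named.

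In 9.3, reconcile the not-modelled list with 10.5.

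The cost is a few lines of SAP text and standard Stata options, with no new data. Standard errors for the consented group rise by a factor of about 1.05 to 1.22 under the assumed ICCs, so the comparison loses some precision. If deaths do not cluster, the loss is small.

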2.2.3 Safety outcomes

Deaths

Records of all those from whom we obtained consent/assent to examine were flagged at the Medical Research Information Service (MRIS), and assessed in order to identify any differences in mortality between the two groups. For those who died in their RNH we asked the home for a brief description of how they died; for those who died in hospital we extracted this information from their hospital records. Medical members of the study team, blind to participants' allocation, assessed these reports. In the event that any death was deemed to be exercise-related on the basis of these brief reports, we made a detailed assessment as to whether it was related to our programme.

Peripheral fractures

Data on these were collected from two sources (i) aggregated at home level and events counted in all residents, not only those who consented/assented to their data being used. (ii) at the individual level in all residents who provided consent/assent at any time for their medical records (held by the PCT) to be accessed.

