5.2.4 Safety population

For the safety analyses the population is defined as all those in the home at any time during the intervention period with exposure given by the length of time within the home during the intervention period i.e. person months of exposure, which will form the denominator

The safety outcomes are deaths and peripheral fractures, both classified as serious adverse events (SAEs). For deaths the study population is all residents present in the home during the intervention period.

Data on peripheral fractures will be collected in two ways and different populations are defined for each

- a. Events in study participants (data available at the level of the individual)
- b. Events in all residents (data available aggregated at the level of home).

For deaths and for peripheral fractures where the event is measured on all participants the denominator is person years of exposure. This allows us to include residents who were neither present at the beginning nor the end of the study.

Barts and The London School of Medicine and Dentistry

Pragmatic Clinical Trials Unit

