We will present the number of deaths for which any injury, i.e. any underlying of contributory cause of death includes an ICD10 code that starts with an 'S', has contributed to the cause of death. We will present these as fracture-related deaths per year of exposure. We will estimate difference in fracture related death rate within a 95% confidence interval.

For the primary cause of death outcome the underlying cause of death from the MRIS data will be used. This will presented as number of deaths during study period, subdivided by ICD chapters; i.e. the first character in the ICD code, between each group. No statistical analyses will be presented.

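### Table 6 sorts only injury-coded deaths and fractures into direct and indirect, so no planned output would show a non-injury death during a class or assessment as directly attributable

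*SAP*

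**What the plan says.** **Definitions.** SAP section 10.5 counts as a serious adverse event anything that "results in death or is life threatening or requires hospitalisation", among other criteria, and sets no limit on cause. It then separates direct from indirect events by circumstance alone: "SAEs can be classified as directly attributable (i.e. occur during a study assessment or getting to or from or occur during a group-activity session"; anything else between randomisation and the end of follow-up is indirect. Section 5.2.4 agrees: "The safety outcomes are deaths and peripheral fractures, both classified as serious adverse events (SAEs".

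**The classification table.** Table 6 applies the direct/indirect split. Its title is "Classification of anonymised fracture-related deaths, and fractures data", and the footnote to its deaths entry reads "fracture-related deaths (ICD10 chapter S". The text after the table gives the rule for identifying these deaths: any underlying or contributory cause "includes an ICD10 code that starts with an 'S', has contributed to the cause of death".

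**Other handling of deaths.** Section 2.2.3 has medical members of the team, blind to allocation, assess reports of how participants died. It continues "In the event that any death was deemed to be exercise-related on the basis of these brief reports", with a detailed assessment of whether the death was related to the programme. Section 10.5 also plans a comparison of total death rates by arm, Kaplan-Meier plots and log-rank tests for consented or assented residents, and counts by ICD chapter. Of those chapter counts it says "No statistical analyses will be presented".

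**The concern.** The definitions are neutral as to cause, but the table that applies them is not. Title and footnote agree with each other, so the restriction looks deliberate and is not a slip in one line.

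The trial tests exercise classes in care-home residents aged 65 or over. Whether anyone died during a class, from any cause, is a basic safety question, and a sudden non-injury death on exertion is an obvious example. A reader of the trial report would expect the direct/indirect classification to answer it. As specified, the classification answers only for deaths with an injury code, and its label does not warn that other deaths in class were never eligible.

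**Working it through.** No arithmetic applies; the SAP attaches no figure to this table. The check follows hypothetical events through the rules as written.

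1. **A participant in an intervention home dies of a cardiac cause during a class, with no S code among the causes.** Under the definition in 10.5 this is a serious adverse event, because it results in death, and it is direct, because it occurs in a group session. Under the title and footnote of Table 6 it is out of scope. Definition and table disagree.
2. **The same death, with an S code recorded as a contributory cause.** It enters Table 6 as direct, because the rule accepts contributory causes. No disagreement.
3. **A participant in a control home dies of a non-injury cause during a study assessment.** It is direct by definition and out of scope of Table 6. Definition and table disagree.
4. **A participant sustains a peripheral fracture during a class.** It is direct by definition and direct in Table 6. No disagreement.

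Next, does any other planned output carry the attribution for events 1 and 3?

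| Output or process in the SAP | Includes the death? | Shows it as direct? |
|---|---|---|
| Table 6 (10.5) | No | No |
| Total death rate by arm (10.5) | Yes | No |
| Kaplan-Meier and log-rank (10.5) | Yes, if consented or assented | No |
| Counts by ICD chapter (10.5) | Yes | No |
| Injury-coded deaths per year of exposure (10.5) | No | No |
| Blinded review of death reports (2.2.3) | Yes | Assessed case by case, but no count, table or listing is specified |

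Section 10.2 says that adverse event data were not collected, so no general adverse event table fills the gap.

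One row of Table 6 needs separate thought: people outside the study who took part in exercise. Section 10.5 takes all cause-of-death data from coding by the Medical Research Information Service. Section 2.2.3 describes flagging there only for those who gave consent or assent. Section 10.5 adds that the data on all residents lack accurate dates of death and resident characteristics. For this row the SAP names no source for an S code, and a full any-cause split may not be possible either.

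**The case against.** The strongest reply is that Table 6 sets out classification rules, not results, and that the general definition above it already makes a cardiac death in a class directly attributable. Nothing in the SAP says that attribution is withheld from events outside the table. The hazard at issue is also handled individually in section 2.2.3, whatever the cause, and for a rare sudden death a case review tells more than a table cell. Section 10.5 undertakes to report and document every resident's death. It also takes its definition of a serious adverse event from a separate reporting protocol that is not shown and may set out how individual events are listed.

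Much of this stands. Three stronger readings might be inferred, and the documents do not support them:

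- **That such a death would be lost or go undetected.** It would be reviewed under 2.2.3 and counted in the mortality outputs shown above.
- **That the trial would report no directly attributable deaths when one had occurred.** Table 6 alone could be read that way. A report that also used the general definition and the 2.2.3 review need not be.
- **That the gap can be sized from the mortality of up to 34% per year quoted in section 3.5.** That rate concerns all deaths. The gap concerns non-injury deaths during a class or assessment, for which the documents give no rate. Most other deaths would be indirect by default, so leaving them out of the table loses little.

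What the reply does not remove is that the SAP's only direct/indirect classification is narrower than its own definition, and that the SAP does not say how the result of the 2.2.3 review will be presented.

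**Conclusion.** The point holds as a gap in attribution and reporting. A non-injury death during a class or assessment meets the SAP's definition of a directly attributable serious adverse event, is excluded from the one classification that uses that definition, and appears in the other planned outputs without attribution. This is a stated restriction that conflicts with sections 5.2.4 and 10.5, and not merely a detail left unsaid.

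No numerical size can be given. The consequence does not depend on frequency, since one such death would make the classification incomplete. The efficacy analyses are unaffected. The conclusion assumes that Table 6 will be reported as titled and footnoted, and that the reporting protocol cited in 10.5 does not already require a listing of directly attributable deaths from any cause. It is worth correcting before the safety results are tabulated.

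**What to change.** Reconcile Table 6 with the definitions in 10.5 and 5.2.4 and with the review in 2.2.3:

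- Remove the chapter S restriction from the title and footnote. For consented or assented participants, classify deaths from any cause as direct or indirect, by arm.
- Show fractures in separate rows, and keep S-coded deaths as a sub-count of all deaths so that the planned injury-related figure is preserved.
- Report by arm the number of deaths judged exercise-related in the 2.2.3 review, whatever their cause.
- For non-participants who took part in exercise, list only deaths known to have occurred during a session, because dates and characteristics are not otherwise available for them.

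The cost is a small amount of extra tabulation. For participants it draws mainly on death reports that section 2.2.3 already has reviewed, and it needs no new statistical model.

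### Section 10.5 of the SAP counts deaths with any injury code but labels them, and compares them between arms, as fracture-related deaths

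*SAP*

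**What the plan says.** The relevant text is in SAP section 10.5, in the part on cause-of-death data and in Table 6.

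- **Source.** "All cause of death data will be based on ICD10 coding provided by MRIS". The same section says that both the underlying cause and the contributing factors are supplied.
- **Case definition.** The count begins "We will present the number of deaths for which any injury" contributed, and is made operational as deaths where "any underlying of contributory cause of death includes an ICD10 code that starts with an" S.
- **Label.** The next sentence reads "We will present these as fracture-related deaths per year of exposure".
- **Comparison.** "We will estimate difference in fracture related death rate within a 95% confidence interval".
- **Table 6.** The title refers to fracture-related deaths, and the footnote to its deaths entry defines them as "fracture-related deaths (ICD10 chapter S".

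**The concern.** The plan's own gloss on the code set is injury, while its reporting label is fracture. A programmer following section 10.5 literally would count every death with an S code and print it under a fracture heading.

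This matters because the trial has little other harm information. Section 10.2 states that adverse event data were not collected, and sections 2.2.3 and 5.2.4 limit the safety outcomes to deaths and peripheral fractures. Section 2.2.2 uses peripheral fractures as the marker for injurious falls. A fracture-related death rate would therefore be one of the few harm figures on view, printed near a separately modelled peripheral-fracture rate. Readers would take it at its word.

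**Working it through.** **Is there a figure to reproduce?** No. The SAP gives no death count, no expected rate and no power for this outcome. The check is of definition against label, followed by an illustration.

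**Step 1: definition against label.**

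| Place in section 10.5 | What is counted | What it is called |
|---|---|---|
| Text, definition sentence | any injury; any underlying or contributory S code | (not yet named) |
| Text, next sentence | the same deaths | fracture-related deaths |
| Text, comparison sentence | the same deaths | fracture-related death rate |
| Table 6 footnote | chapter S | fracture-related deaths |

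No step between the first row and the others removes non-fracture injuries. The mismatch occurs in both the text and the table, so it is not a slip in one sentence.

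**Step 2: does another sentence withdraw the comparison?** The section ends by saying that no statistical analyses will be presented. That closes a different paragraph, which opens "For the primary cause of death outcome the underlying cause of death from the MRIS data will be used" and tabulates underlying cause by ICD chapter. The rate difference and its interval stand.

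**Step 3: effect on the rate.** Let N be the number of S-coded deaths and D the number of deaths truly involving a fracture. Let f be the share of S-coded deaths that involve a fracture, and s the share of fracture deaths that carry an S code. Deaths in both sets can be counted two ways, f × N = s × D, so

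reported rate / true fracture-related rate = N / D = s / f.

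Both s and f are assumptions; the SAP gives neither.

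| | f = 0.5 | f = 0.7 | f = 0.9 | f = 1.0 |
|---|---|---|---|---|
| s = 1.0 | 2.00 | 1.43 | 1.11 | 1.00 |
| s = 0.9 | 1.80 | 1.29 | 1.00 | 0.90 |
| s = 0.8 | 1.60 | 1.14 | 0.89 | 0.80 |

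The rate is too high only when s exceeds f. If some fracture deaths lack an S code, it can be too low.

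**Step 4: effect on the comparison.** If s and f are the same in both arms, each arm's rate is multiplied by s / f. The rate ratio is unchanged, but the rate difference, which is the planned quantity, is multiplied by s / f. More generally, write each arm's reported rate as s × λ + ν, where λ is its fracture-related death rate and ν its rate of S-coded deaths without a fracture. With s equal in both arms, the reported difference is s × (λ₁ − λ₀) + (ν₁ − ν₀). It equals the fracture-related difference only in special cases, such as s = 1 with ν₁ = ν₀. Nothing in the SAP tells us which case applies.

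**The case against.** The strongest reply is that this is only a naming matter. The coding rule is pre-specified and stated openly, so a report that repeats it would tell readers what was counted. The same rule applies in both arms. Fracture-related death is not among the safety objectives in section 2.1.3, which are peripheral fractures and mortality. Both have their own analyses in section 10.5: a mixed Poisson model for fractures, and log-rank and related methods for deaths. The review of death reports blind to allocation (section 2.2.3) does not use the S-code rule.

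Most of this stands, and it limits the scope of the point. It does not remove the contradiction: the plan never says that S is meant as a broad proxy for fracture, and a plan that means injury should say injury.

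Four stronger readings are tempting and are not supported:

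- **That the rate is tested.** Only an estimated difference with an interval is planned. The general rule, "All analyses will be conducted two-sided and significance interpreted at the 5% level", may lead a reader to treat the interval as a test, but no test or p-value is named for this quantity.
- **That the fracture-related rate is overstated.** This is a natural expectation, but it requires s to exceed f, and the SAP shows neither share.
- **That the comparison is biased for or against exercise.** Step 4 shows that this depends on how injury deaths divide in each arm, which the SAP does not give.
- **That Table 6 should be restricted to fracture deaths.** That would drop non-fracture injury deaths from the direct/indirect attribution and so narrow the safety record. Attribution depends on whether the event occurred during assessment or exercise, not on the type of injury.

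**Conclusion.** The point holds as a contradiction between definition and label, in the section 10.5 text and in Table 6. Followed exactly, the plan produces an injury-related death rate and rate difference presented as fracture-related. If every S-coded death in the trial involved a fracture and every fracture death carried an S code, the figures would coincide; the SAP gives no ground for assuming so.

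The size and direction of the error cannot be computed from the SAP. The ratios of 0.80 to 2.00 illustrate assumed shares and are not estimates. The error is confined to this one safety summary. It is nonetheless more than a typographical slip, because it changes what can be concluded from a published harm figure.

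**What to change.** 1. In the section 10.5 text, the Table 6 title and its footnote, rename the S-code outcome injury-related deaths. Keep all S-coded deaths in Table 6 and in the rate difference with its 95% interval.
2. If a fracture-related death rate is also wanted, report it as a second line, defined by a list of fracture codes written into the SAP before analysis. Fixing the list in advance matters because section 5.1 says the study statistician is not blinded.

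**Cost.** The first change is a relabelling in three places. The second needs a code list and one more row. Neither needs new data, since MRIS supplies the underlying and contributing codes. The downside is that the fracture line will have fewer events and a wider interval than the injury line.
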